5.3 Lifestyle Considerations

No restrictions with regard to lifestyle are required.

5.4 Screen Failures

Screen failures are defined as subjects who consent to participate in the clinical study but are not subsequently randomly assigned to study treatment/entered in the study. A minimal set of screen failure information is required to ensure transparent reporting of screen failure subjects to meet the Consolidated Standards of Reporting Trials (CONSORT) publishing requirements and to respond to queries from regulatory authorities. Minimal information includes demography, screen failure details, eligibility criteria and any SAE.

Individuals who do not meet the criteria for participation in this study (screen failure) may be rescreened once after discussion with the Medical Advisor/Sponsor Medical Representative. Rescreened subjects should not be assigned the same subject number as for the initial screening.

Safety assessments that are measured and do not meet the inclusion/exclusion criteria may be repeated once without the subject being considered a screen failure.

Subjects who are rescreened more than 2 weeks after their first screen will have all assessments repeated.

6.0 STUDY TREATMENT

Study treatment is defined as any investigational treatment(s), marketed product(s), placebo or medical device(s) intended to be administered to a subject according to the study protocol.

6.1 Study Treatment(s) Administered

Table 5Study Treatment Details

Study Treatment Name:	Namilumab	Placebo
Dosage Formulation:	Solution for injection	Solution for injection
Unit Dose Strength(s)/Dosage Level(s):		
Route of Administration:	Subcutaneous	Subcutaneous
Dosing Instructions:		
Packaging and Labelling:	Supplies of namilumab will be labelled according to local regulations.	Supplies of placebo will be labelled according to local regulations

6.2 Preparation/Handling/Storage/Accountability

6.2.1 Preparation

All IMPs are provided in sterile, single-use glass vials.

. Each carton and vial

will be labelled with a unique medication identification (MED ID) number and will be dispensed via an interactive web response system (IWRS).

6.2.2 Handling

All study medications will be administered by the Investigator or designee.

The subject will visit the clinic for dosing of **binded** of blinded study medication by a single subcutaneous injection on Days 1, 15, 43 and 71.

6.2.3 Storage

The Investigator or designee must confirm that appropriate temperature conditions have been maintained for all clinical trial material received and that any discrepancies are reported and resolved before use.

The clinical trial material must be stored according to the manufacturer's stipulation, as specified on the label.

During shipping, vials will be protected from light and maintained between Each shipment will include a packing slip listing the contents of the shipment, and any applicable forms.

All clinical trial material must be kept in an appropriate, limited-access, secure location until used or returned to the sponsor or designee. All study medication must be stored under the conditions specified on the label and remain in the original container until dispensed. A daily temperature log of the drug storage area must be maintained every day.

The Investigator or designee must confirm that appropriate temperature conditions have been maintained for all clinical trial material received and that any discrepancies are reported and resolved before use.

The Investigator is responsible for ensuring that deliveries of clinical trial material from the sponsor are correctly received, recorded, and handled, and stored safely and properly in accordance with the Code of Federal Regulations (CFR) or national and local regulations, and used in accordance with this protocol.

The Sponsor must be notified immediately of any temperature excursions, shipping and handling or storage discrepancies.

Drug supplies will be counted and reconciled at the site before being returned to Takeda or designee or being destroyed.

6.3 Measures to Minimise Bias: Randomisation and Blinding

6.3.1 Investigational Drug Assignment and Dispensing Procedures

Study medication will be provided in a blinded fashion and dispensed in accordance with randomisation code. Randomisation will be performed by IWRS. Before the study is initiated, the log-in information and directions for the IWRS will be provided to each study site. Study treatment will be dispensed at the study visits as summarised in the Schedule of Activities (SoA). Returned study treatment must not be re-dispensed to subjects.

The Investigator or Investigator's designee will access the IWRS at Screening to obtain the subject study number. The Investigator or the Investigator's designee will utilise the IWRS to randomise the subject into the study. During this contact, the Investigator or designee will provide the necessary subject-identifying information, including the subject number assigned at screening. The MED ID number of the study medication to be dispensed will then be provided by the IWRS. If the MED ID number is lost or damaged, the site can request a replacement from the IWRS. (Refer to the IWRS manual provided separately). The MED ID number will be entered onto the electronic case report form (eCRF). At all drug-dispensing visits, the Investigator or designee will again contact the IWRS to request additional investigational drug for a subject.

6.3.2 Randomisation Code Creation and Storage

The randomisation schedule will be created by the Sponsor or designee and stored in a secure area, accessible only to authorised personnel. Block sizes will be specified in the randomisation specifications. Randomisation will be stratified by prior use of anti-TNF agents.

6.3.3 Investigational Drug Blind Maintenance

Products are not visually identical, however, to protect the blind, a clear yellow label will be applied to the cover of the syringe prior to the drug product being drawn from the vial. Vials and cartons will be supplied with a blinded label, randomisation will be unblinded and dispensation will be completed by an unblinded pharmacist.

The IMP blind will be maintained using the IWRS, which can be accessed and broken by the Investigator or designee in an emergency for unblinding of study medication assignments to ensure the safety of the subject.

6.3.4 Unblinding Procedure

The IMP blind shall not be broken by the Investigator unless information concerning the investigational drug is necessary for the medical treatment of the subject. In the event of a medical emergency, if possible (but not required), the medical monitor should be contacted before the IMP blind is broken to discuss the need for unblinding and if unblinding is required.

For unblinding a subject, the IMP blind can be obtained and broken by the Investigator at any time, by accessing the IWRS.

The Sponsor must be notified as soon as possible if the IMP blind is broken. The date, time and reason for the blind being broken must be recorded in the eCRF.

If any site personnel are unblinded to a subject's treatment, investigational drug must be stopped immediately and the subject must be withdrawn from the study. The Investigator or other site personnel should not reveal the specific treatment assignment of the unblinded subject to the medical monitor or other contract research organisation (CRO) or Sponsor staff. The subject should continue to the EoT/Early Termination (ET) Visit.

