The study will consist of a maximum 4-week Screening Period, followed by a 12-week double-blind treatment evaluation period, followed by a 16-week safety follow-up period, for a maximum study duration of approximately 32 weeks or 224 days per subject. Eligible subjects will be randomised on Day 1 of Week 0 and receive study treatment administered sc on Day 1 of Week 0, Week 2 (loading dose), Week 6 and Week 10. Subjects will return on Week 12 for an End of Treatment (EoT) visit during which efficacy and safety assessments will be performed. Subjects will have a follow-up visit 16 weeks after the EoT visit.

Number of Investigators and Study Centres:

Up to 10 Investigators and 10 study centres are expected to participate in this study.

Number of Subjects:

Approximately 70 subjects will be screened to achieve 42 subjects randomly assigned to study treatment (36 on active treatment and 6 on placebo) and 42 evaluable subjects for an estimated total of 36 evaluable subjects on the active treatment arm and 6 evaluable subjects in the placebo treatment arm.

Treatment Groups and Duration:

Test product, dose and mode of administration:

Namilumab 150 mg sc administered at Weeks 0, 2, 6 and 10.

Reference therapy, dose and mode of administration:

Matching placebo solution sc administered at Weeks 0, 2, 6 and 10.

Statistical Methods:

The primary endpoint will be ASAS20. Based on literature data, the prior for the placebo and namilumab groups will follow a beta distribution with mean of 0.3 and 0.6, respectively. Weighting for the priors will be equivalent to 20 and 5 subjects, respectively. Sample size is the smallest sample size so that P{ θ act > θ pbo| Y(HA)} >0.927 with probability 0.9, assuming true response rates of 0.3 and 0.6 for the control and namilumab arms, respectively. For a 6:1 randomisation, 42 patients need to be randomised.

Efficacy endpoints will be summarised by treatment group and visit. The posterior distribution of the primary endpoint will be computed using the conjugate priors, and the mean, standard deviation, and 5th, 10th, 25th, 50th, 75th, 90th, and 95th percentiles of the posterior distribution will be presented.

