AE=adverse event; ANA=anti-nuclear antibody; ASDAS=Assessment of SpondyloArthritis Disease Activity Score; BASDAI=Bath Ankylosing Spondylitis Disease Activity Index; BASFI=Bath Ankylosing Spondylitis Functional Index; CRP=C-reactive protein; ECG=electrocardiogram; EoT=End of Treatment; ESR=erythrocyte sedimentation rate; ET=Early Termination; FU=Follow-up; GM-CSF=granulocyte-macrophage colony-stimulating factor; Hep=hepatitis; HIV=human immunodeficiency virus; IMP=investigational medicinal product; MRC=Medical Research Council; MRI=magnetic resonance imaging; PAP=pulmonary alveolar proteinosis; PD=pharmacodynamic; PK=pharmacokinetic; WOCBP=women of childbearing potential.

- 1. Screening may be a maximum 4 weeks prior to baseline for some subjects (where stabilisation/wash-out of concomitant medication is needed) and only 1 week prior to baseline for subjects that already meet all inclusion/exclusion criteria).
- 2. Subjects who discontinue the study prior to the EoT visit should attend the EoT/ET visit and follow the schedule for the FU period.
- 3. One FU telephone contact will be performed between study completion and end of study visit approximately 6 weeks after last dosing; AE and concomitant medication will be collected.
- 4. In the treatment period, both pre-dosing and post-dosing (approximately 30 minutes post-dosing) vital sign assessments are to be performed.
- 5. Blood draw for evaluation of CRP and ESR only.
- 6. Pregnancy testing at Screening will be in serum; pregnancy testing at other visits will be in urine; a positive urine test will be confirmed with a serum pregnancy test.
- 7. Lung function tests includes: FEV₁, FVC and PEF.
- 8. Chest x-ray within 3 months of Screening to assess for PAP.
- 9. The pre-dosing MRI can be performed within 6 months before Screening.
- 10. Although the post-dosing EoT MRI is scheduled to occur at the week 12 visit, the MRI may be performed between weeks 12 and 16 if possible for study centres with logistical issues that prevent performing the MRI at the week 12 visit. The EoT MRI is optional; however, the study centres are requested to perform the EoT MRI on all subjects to the extent possible.
- 11.PK/PD sampling must be taken pre-dose (t=0).
- 12. Stored sample for immunogenicity assessment for evaluation of anti-namilumab antibodies.
- 13.Immunology assessment for evaluation of ANA (anti-dsDNA if ANA is positive).
- 14.HLA-B27 testing will only be performed in subjects whose HLA-B27 status is unknown.

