7.2 Subject Discontinuation/Withdrawal from the Study

A subject may withdraw from the study at any time at his/her own request or may be withdrawn at any time at the discretion of the Investigator for safety, behavioural, compliance or administrative reasons.

If the subject withdraws consent for disclosure of future information, the Sponsor may retain and continue to use any data collected before such a withdrawal of consent.

If a subject withdraws from the study, he/she may request destruction of any samples taken and not tested, and the Investigator must document this in the study centre study records.

See SoA for data to be collected at the time of study discontinuation and follow-up and for any further evaluations that need to be completed.

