8.3.1 Time Period and Frequency for Collecting AE and SAE Information

All SAEs will be collected from the signing of the ICF until the follow-up visit at the time points specified in the SoA (Section 1.3).

All AEs will be collected from the signing of the ICF until the follow-up visit at the time points specified in the SoA (Section 1.3).

All SAEs will be recorded and reported to the Sponsor or designee within 24 hours, as indicated in Appendix 4. The Investigator will submit any updated SAE data to the Sponsor within 24 hours of it being available.

Investigators are not obligated to actively seek AE or SAE after conclusion of the study participation. However, if the Investigator learns of any SAE, including a death, at any time after a subject has been discharged from the study, and he/she considers the event to be reasonably

related to the study treatment or study participation, the Investigator must promptly notify the Sponsor.

The method of recording, evaluating and assessing causality of AE and SAE and the procedures for completing and transmitting SAE reports are provided in Appendix 4.

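### For a subject unblinded after the Week 12 visit, Section 6.3.4 ends study participation and no passage keeps the Week 28 safety visit

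*Protocol*

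**What the plan says.** Protocol Section 6.3.4 permits the Investigator to break the blind only for medical need ("unless information concerning the investigational drug is necessary for the medical treatment of the subject"), but places no limit on when: "the IMP blind can be obtained and broken by the Investigator at any time". Once any site staff are unblinded, "investigational drug must be stopped immediately and the subject must be withdrawn from the study". The one visit the section then preserves is this: "The subject should continue to the EoT/Early Termination (ET) Visit".

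Two other places bear on what happens next. Footnote 2 of the Schedule of Activities (Section 1.3) reads: "Subjects who discontinue the study prior to the EoT visit should attend the EoT/ET visit and follow the schedule for the FU period". Section 7.2, on withdrawal from the study, adds no rule of its own: "See SoA for data to be collected at the time of study discontinuation and follow-up and for any further evaluations that need to be completed".

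The planned follow-up is set out in the Synopsis: "Subjects will have a follow-up visit 16 weeks after the EoT visit". On AE collection, Section 8.3.1 runs it to the follow-up visit, but also says: "Investigators are not obligated to actively seek AE or SAE after conclusion of the study participation".

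**The concern.** Section 6.3.4 joins two consequences, stopping drug and leaving the study, and applies both whenever the blind is broken. In the 16 weeks after EoT dosing is already complete, so only the second has any effect. Read as written, it takes out of scheduled safety follow-up a subject whose blind was broken because of a medical problem, while the antibody is still being cleared and while new AEs would still count as treatment-emergent.

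Safety is a secondary objective, and the plan has 36 namilumab and 6 placebo subjects, so each incomplete follow-up matters. Authorised unblinding is tied to medical need, so those affected would not be a random subset.

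**Working it through.** **Inputs (nominal days)**

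| Item | Value | Source |
|---|---|---|
| First and last dose | Day 1, Day 71 | Protocol 6.2.2; Schedule of Activities |
| EoT visit | Day 85 | Schedule of Activities |
| Follow-up telephone contact | about 6 weeks after last dose | Schedule of Activities, footnote 3 |
| Week 28 visit | Day 197 | Schedule of Activities |
| Treatment-emergent AE window | 125 days after last dose | Protocol 9.4.2; SAP 15.1 |

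**Step 1. Reproduce the stated follow-up length.** 197 − 85 = 112 days, and 112 / 7 = 16 weeks, as the protocol states. This is 112 / (197 − 1) = 112 / 196 = 57% of the time from first dose to final visit.

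**Step 2. Is there drug left to stop after EoT?** The last dose (Day 71) precedes EoT (Day 85) by 14 days. After EoT the drug-stopping half of the sentence has nothing to act on, and withdrawal from the study is its only operative effect.

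**Step 3. Compare with the AE window.** 71 + 125 = Day 196, one day before the Week 28 visit. A subject unblinded on Day 86 would lose 197 − 86 = 111 days of planned follow-up. Later unblinding loses less, and 112 days is the outer bound. The telephone contact falls at about 71 + 42 = Day 113, so it is also lost if the blind is broken before then.

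**Step 4. Set the passages side by side.**

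| Question | Unblinded before EoT | Unblinded between EoT and Week 28 |
|---|---|---|
| Visit kept by 6.3.4 | EoT/ET | None remaining: EoT has passed |
| Footnote 2 | Applies: EoT/ET visit, then follow-up schedule | Does not apply: limited to leaving before EoT |
| Section 7.2 | Points to the schedule, which has a rule | Points to the schedule, which has no rule for this case |
| Active AE collection (8.3.1) | Continues through follow-up | Not required once participation ends |

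**Step 5. What the Week 28 visit carries.** Physical examination, vital signs, ECG, pulse oximetry, MRC breathlessness scale, chest x-ray and AE collection. Spirometry is not scheduled then, so none is lost.

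**Step 6. What still continues after withdrawal.** SAEs and AEs of special interest are followed to an outcome (8.3.3), as is suspected PAP (8.2.5). Clinically significant laboratory abnormalities arising within 18 weeks of the last dose are repeated (8.2.8; 71 + 126 = Day 197). Related SAEs that the Investigator learns of are reported (8.3.1). A final-visit serum sample is requested from withdrawn subjects (8.8.1). All but the last act on an event or abnormality that has already come to light. None restores the scheduled contacts or the Week 28 visit.

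**The case against.** The strongest reply is that Section 6.3.4 was written for the treatment period. Stopping drug and continuing to EoT/ET both assume a subject who has not reached EoT. For that subject footnote 2 is explicit and is itself worded for people who leave the study, so it states what withdrawal entails rather than conflicting with it. Section 9.4.4 also expects follow-up data from withdrawn subjects in the analysis. On this view the protocol intends follow-up to continue, and the gap is a matter of drafting.

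Much of this stands. Before EoT the follow-up schedule is kept, and no sentence expressly cancels Week 28 for anyone. But 6.3.4 lets the blind be broken at any time and makes withdrawal mandatory, so a site following the text after EoT would end participation and find no instruction to the contrary.

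A reader might infer more than the documents support:

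- **That anti-drug antibody data go unrecorded.** Section 8.8.1 asks for a serum sample at the final visit of withdrawn subjects. At most its timing changes.
- **That the safety denominator shrinks, weakening the bound on PAP incidence.** A subject unblinded after EoT has passed the whole dosing period and the Week 12 assessments, including the chest x-ray if performed as scheduled, and stays in the Safety Analysis Set.
- **That the safety profile is biased towards looking cleaner.** The selection is plausible, but the documents give no unblinding rate and nothing from which to size a bias. The triggering event is recorded in any case. Section 8.3.6 expects PAP symptoms only after years of disrupted signalling, though it also says x-ray changes come before severe symptoms.

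**Conclusion.** The point holds for unblinding between EoT and Week 28, and only there. In that interval the protocol's wording ends scheduled safety collection up to 112 days early, within a treatment-emergent AE window that runs to Day 196, and has no other effect. The loss is of new or unsolicited findings and of the Week 28 examinations. Events already known remain followed.

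This rests on taking withdrawal from the study at its ordinary meaning and on nominal visit days. The number of subjects affected cannot be estimated from the documents and is presumably small. The Week 12 primary endpoint, its non-responder rule and the sample size are not touched. It is a modest but real defect, worth correcting because the correction costs so little.

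**What to change.** Reconcile Section 6.3.4, footnote 2 of the Schedule of Activities and Section 7.2 for unblinding after EoT:

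- In 6.3.4, separate study participation from study drug, so that unblinding does not by itself end participation.
- In footnote 2, extend the retention wording to subjects who are unblinded or discontinue after EoT, so that those who consent remain in the telephone contact (if still due) and the Week 28 visit.
- Section 7.2 can keep its pointer, because the schedule would then contain the rule it points to.

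The change concerns participation and data collection only. It takes no position on when drug should be stopped, and efficacy handling stays as planned. The cost is about two sentences in a protocol amendment, with no visits or procedures beyond those already scheduled for every subject.

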6.3.5 Accountability and Destruction of Sponsor-Supplied Drugs

Drug supplies will be counted and reconciled at the site before being returned to the Sponsor or designee, or before being destroyed at the site (if approved by the Sponsor for destruction at the site).

The Investigator or designee must ensure that the clinical trial material is used in accordance with the approved protocol and is dispensed only to subjects enrolled in the study. To document appropriate use of the clinical trial material, the Investigator must maintain records of all

Sponsor-supplied drug delivery to the site, site inventory, dispensation and use by each subject, and return to the Sponsor or designee.

Upon receipt of the clinical trial material, the Investigator or designee must verify the contents of the shipments against the packing list. The verifier should ensure that the quantity is correct, and that the medication is received within the labelled storage conditions in good condition. If there are any discrepancies between the packing list versus the actual product received, the Sponsor must be contacted to resolve the issue. The packing list should be filed in the Investigator's essential document file.

The Investigator must maintain 100% accountability for all clinical trial material received and dispensed during his or her entire participation in the study. Proper drug accountability includes, but is not limited to:

- Frequently verifying that actual inventory matches IWRS inventory.
- Verifying that the IWRS is completed for the MED ID used to prepare each dose.
- Verifying that all containers used are documented accurately in the IWRS.
- Verifying that required IWRS fields are completed accurately.

If any dispensing errors or discrepancies are discovered, the Sponsor must be notified immediately.

The current inventory of all clinical trial material at sites will be tracked through the IWRS.

The IWRS will include all required information as a separate entry for each subject to whom clinical trial material is dispensed.

The Investigator will be notified of any expiry date extension for clinical trial material during the study conduct. On expiry date notification from the Sponsor or designee, the site must complete all instructions outlined in the notification including segregation of expired clinical trial material for return to the Sponsor or its designee for destruction.

In the event of expiry date extension of supplies already at the study site, supplies may be relabelled with the new expiry date. In such cases, the Sponsor or its designee will prepare additional labels and all necessary documentation for completion of the procedure.

